13.6 Analysis of Secondary Endpoints

The secondary end-point of this study is the change in exercise duration with ivabradine, compared to placebo, in survivors of lymphoma with mediastinal involvement who were treated with mediastinal/mantle radiation and have a resting HR \geq 80 bpm.

We will calculate the change in exercise duration (from exercise treadmill stress tests) from baseline to 6 weeks for each patient in the study (n=60). An ANCOVA model (for normally distributed data) adjusting for the stratification factors (beta blocking agents [Yes, No], autonomic function testing [Yes, No]) or Quade test adjusting for the stratification factors (beta blocking agents [Yes, No], autonomic function testing [Yes, No]) (for non-normally distributed data) will be implemented to compare the change in exercise duration with ivabradine versus placebo.

We will then repeat the analysis with change in resting HR as an additional independent variable to assess whether change in resting HR affects exercise duration. A p value < 0.05 using a two-sided test will be considered statistically significant.

Exploratory end-points of this study are:

- 1) Change in additional markers of cardiac sympatho-vagal balance with ivabradine, compared to placebo, in survivors of lymphoma with mediastinal involvement who were treated with mediastinal/mantle radiation and have a resting HR \geq 80 bpm.

Since this is an exploratory end-point and due to cost constraints, it will only be conducted in half the patients enrolled in the trial (n=30) and no power calculation has been made. The cardiovagal composite autonomic severity score (CASS) and adrenergic CASS will be calculated at baseline and at 6 weeks (as described in Section 5.3.3) for each patient in this substudy. The change in CASS and adrenergic CASS will then be assessed for each patient. Quade test adjusting for the stratification factors (beta blocking agents [Yes, No], autonomic function testing [Yes, No]) (for ordinal data) will be implemented to compare the change in CASS and adrenergic CASS in patients treated with ivabradine versus placebo. A p value < 0.05 using a two-sided test will be considered statistically significant.

- 2) Change in health related quality of life with with ivabradine, compared to placebo, in survivors of lymphoma with mediastinal involvement who were treated with

mediastinal/mantle radiation and have a resting HR \geq 80 bpm.

All patients (n=60) will complete the SF-36 health survey at baseline and at 6 weeks. The SF-36 questionnaire consists of eight subsections; physical functioning, social role functioning, physical role functioning, emotional role functioning, mental health, vitality, bodily pain, and general health perceptions. For each section, item scores are coded from 0 (worst health status) to 100 (best health status). Total scores are also obtained for two main domains: a physical component -consisting of physical function, role physical, bodily pain, and general health subscales- and a mental component -consisting of role emotional, social functioning, mental health, and vitality. SF-36 has been used to assess quality of life in several cancer populations. Change in SF-36 scores from baseline to 6 weeks will be calculated for each patient. An ANCOVA model (for normally distributed data) adjusting for the stratification factors (beta blocking agents [Yes, No], autonomic function testing [Yes, No]) or Quade test adjusting for the stratification factor (beta blocking agents [Yes, No], autonomic function testing [Yes, No]) (for non-normally distributed data) will be implemented to compare the change in quality of life with ivabradine versus placebo. A p value $<$ 0.05 using a two-sided test will be considered statistically significant.

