Ivabradine is well tolerated with a similar incidence of adverse effects when compared to placebo in a large (n=6,505) clinical trial involving patients with chronic systolic heart failure (SHIFT: Systolic Heart Failure Treatment with the I_f Inhibitor Ivabradine Trial).¹⁷ It is approved by the FDA to decrease heart failure related deaths and hospitalizations in patients with systolic heart failure (LVEF ≤ 35%) who have a resting HR ≥ 70 beats per minute despite maximal tolerated doses of beta-blockers. We wish to investigate whether ivabradine can achieve HR reduction in patients with a resting heart rate ≥ 80 bpm as a consequence of thoracic RT irrespective of baseline LVEF, and if so whether observed reductions in HR translate into improvements in exercise capacity. In addition, we wish to investigate whether ivabradine improves cardiac sympatho-vagal balance and patient-reported quality of life in this cohort. To date, this will be the first randomized trial of any therapeutic agent in the management of these patients. We will use a dose scheme similar to that used in the SHIFT trial.¹⁷

Matching placebo tablets will be manufactured and supplied by the Investigational Drug Pharmacy at Brigham and Women's Hospital.

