5.3.1 CTEP and/or CIP IND Agent(s), or other IND agent: N/A

5.3.2 Other Agent(s): N/A

5.3.3 Other Modality(ies) or Procedures

All patients will have a standard 12 lead EKG performed at the screening, baseline, 2 week and 6 week visits.

All patients will undergo exercise treadmill testing at the baseline and 6 week visits.

All patients will have a 24 hour ambulatory Holter monitor placed at the baseline and 6 week visits.

All patients will complete the SF-36 quality of life questionnaire at the baseline and 6 week visits.

Due to cost constraints, a subset of patients (n=30) will undergo further sophisticated autonomic function testing at the baseline and 6 week visits. Depending on scheduling limitations, they may have to return for a second day at each of these visits to complete the additional autonomic function tests.

a) Exercise treadmill testing

All exercise stress tests will be performed in the cardiovascular stress testing laboratory at Brigham and Women's Hospital by trained exercise physiologists under the supervision of a staff

cardiologist. Patients will avoid consumption of all caffeine containing products for 24 hours prior to exercise treadmill testing. All patients will undergo exercise treadmill testing using a symptom-limited Bruce protocol according to established guidelines.¹⁸ Exercise will be continued until one or more of the following endpoints: exhaustion, symptom limitation, $\geq 85\%$ of age-predicted maximal HR, ≥ 10 mmHg drop in systolic blood pressure (SBP) from baseline, sustained ventricular tachycardia, ST-segment depression ≥ 3 mm measured 80 msec after the J junction, or ST-segment elevation of ≥ 1 mm.

b) 24 Hour Ambulatory Holter Monitor

All patients will have a 24 hour ambulatory Holter monitor placed at baseline prior to study drug initiation and at the 6 week time point, prior to study drug termination. Holter monitors will be placed by the cardiology department at Brigham and Women's Hospital. Patients will be asked to return the Holter monitor in person or via mail to Brigham and Women's Hospital.

c) SF-36 Quality of Life Questionnaire

All patients will be asked to complete short form 36 (SF-36) quality of life healthcare questionnaires at the baseline and 6 week visits.

d) Sophisticated autonomic function testing

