13.1 Study Design/Endpoints

Primary End point:

The primary objective of this study is to investigate whether ivabradine lowers resting HR, compared to placebo, in survivors of lymphoma with mediastinal involvement who were treated with mediastinal/mantle radiation and have a resting HR ≥ 80 bpm.

Secondary End-point:

The secondary objective of this study is to evaluate whether ivabradine improves exercise duration, compared to placebo, in survivors of lymphoma with mediastinal involvement who were treated with mediastinal/mantle radiation and have a resting HR ≥ 80 bpm.

Exploratory End-points:

- 1) To evaluate whether ivabradine improves additional markers of cardiac sympatho-vagal balance, compared to placebo, in survivors of lymphoma with mediastinal involvement who were treated with mediastinal/mantle radiation and have a resting HR ≥ 80 bpm.
 - 2) To evaluate whether ivabradine improves health related quality of life, compared to placebo, in survivors of lymphoma with mediastinal involvement who were treated with mediastinal/mantle radiation and have a resting HR ≥ 80 bpm.
- The patients will be accrued on a continuous basis from the out-patient survivorship, cardio-oncology, and radiation oncology clinics at DFCI, Massachusetts General Hospital, Brigham and Women's Hospital, and Boston Children's Hospital till target accrual is completed. Eligible patients from sites other than the Brigham will be referred to the Brigham for all study procedures.
 - There are no explicit early stopping rules for this study. However, the data will be reviewed periodically by the DFCI DSMB and the study will be terminated if the DSMB deems it necessary to do so.
 - The target sample size for this study is 54 patients. We plan to enroll a total of 60 patients to account for screen failure, resting HR < 80 at baseline visit, withdrawals, or loss to follow up. Based on our clinical volume, we plan to recruit 2-3 patients per month over a cumulative accrual period of 24-36 months. Each patient will be followed for the 6 week duration of the study. There is no long-term follow-up planned in this study.
 - We hypothesize that ivabradine will lower resting HR, compared to placebo, in survivors of lymphoma with mediastinal involvement who were treated with mediastinal/mantle radiation

and have a resting HR \geq 80 bpm. We further hypothesize that this reduction in HR will be associated with increased exercise duration in these patients.

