- In the Ivabradine and chronic outcomes in heart failure (SHIFT) trial, the net reduction in heart rate with ivabradine was 10.9 (95% CI 10.4-11.4) bpm, with a standard deviation of 10.5 bpm. Thus, with a sample size of 27 patients in each group, we will have 95% power to detect this net reduction in heart rate assuming a probability of making a type I error of 0.05.¹² To allow for incomplete primary end point data due to withdrawals or loss to follow up, we will aim to recruit 30 patients in each group.
- With a sample size of 27 subjects in each group, we will have 90% power to detect a clinically meaningful improvement of 34% in exercise duration on treadmill testing assuming a probability of making a type I error of 0.05, an improvement in the placebo group of 12%, and a standard deviation of 24%.
- All patients will first be stratified into two groups according to pre-randomization treatment with beta-blocking agents. Patients within each beta-blocker group will then undergo four way randomization using permuted blocks, dividing the two strata into four groups each: ivabradine with sophisticated autonomic testing, placebo with sophisticated autonomic testing, ivabradine with no sophisticated autonomic testing, placebo with no sophisticated autonomic testing. These four groups will be created in a 1:1:1:1 ratio. Randomization will be performed by the ODQ at Dana Farber Cancer Institute.
- If patients are randomized into the sophisticated autonomic testing group and are not able to complete sophisticated autonomic function testing for any reason, but are willing to continue taking the study medication (ivabradine or placebo), they will be encouraged to continue taking part in all other study protocols for the duration of the study: twice daily ivabradine or placebo, history and physical exam, EKG, SF-36 questionnaire, exercise treadmill test, and 24 hour ambulatory holter monitoring.

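### The follow-on exercise model in 13.6 asks whether change in resting HR affects exercise duration, but HR change is a post-randomisation variable and the model can show only an association

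*Combined protocol and SAP*

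**What the plan says.** Section 13.6 compares change in exercise duration between arms, using ANCOVA for normally distributed data or a Quade test otherwise, adjusted for beta-blocker use and assignment to autonomic testing. It will then "repeat the analysis with change in resting HR as an additional independent variable to assess whether change in resting HR affects exercise duration". The next sentence reads "A p value < 0.05 using a two-sided test will be considered statistically significant". It does not say whether this governs the arm comparison, the HR term or the HR-adjusted drug term.

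The added variable is the primary endpoint of Section 13.5, measured over the same interval (baseline to week 6) as the exercise outcome.

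The plan words the link between HR and exercise in two ways:

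- **Causal.** Section 2.3 asks "whether observed reductions in HR translate into improvements in exercise capacity". Section 2.4 and the opening of Section 13 hypothesise that the HR reduction will produce greater exercise capacity.
- **Associational.** Section 13.1 says "We further hypothesize that this reduction in HR will be associated with increased exercise duration in these patients".

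The documents name no mediation method, no assumption about confounding, no further covariates and no exploratory label for this step.

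**The concern.** Randomisation supports two causal statements: the drug's effect on HR and its effect on exercise duration. It does not support a third, the effect of HR change on exercise duration, because patients are not randomised to their HR change. Anything that moves both quantities over six weeks will appear in the HR coefficient. Examples are a change in fitness, an intercurrent illness or a change in beta-blocker treatment.

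The documents themselves point to one shared influence that the model omits. Section 2.3 says the HR reduction is larger when baseline HR is higher. Section 2.1 reports shorter exercise in irradiated survivors with elevated resting HR (9.2 versus 10.7 minutes). Neither baseline HR nor baseline exercise duration is in the model.

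Two conclusions are at stake. A significant HR term could be reported as evidence that lowering HR improves exercise. The drug coefficient beside it could be read as the part of the drug effect that does not run through HR. The design supports neither.

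**Working it through.** **Inputs from Section 13.1.** For HR, "the net reduction in heart rate with ivabradine was 10.9 (95% CI 10.4-11.4) bpm, with a standard deviation of 10.5 bpm". For exercise, the gain is 34% on ivabradine and 12% on placebo, a difference of 22 points, with SD 24%. There are 27 evaluable patients per arm and alpha is 0.05 two-sided.

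**Input not in the documents.** The within-arm correlation between HR change and exercise change that arises from shared causes, written ρ. I take |ρ| from 0 to 0.4 as an assumption.

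**The plan's own figures first.** For a two-sample t-test the noncentrality is d / (SD × √(2/n)), with √(2/27) = 0.272.

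- HR: 10.9 / (10.5 × 0.272) = 3.81, which gives power 96.3% (stated: 95%).
- Exercise: 22 / (24 × 0.272) = 3.37, which gives power 91.1% (stated: 90%).

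Both reproduce, so the inputs are consistent with the plan.

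**Follow-on model.** Exercise change is regressed on arm, the two strata and HR change. If HR has no effect but the within-arm correlation is ρ, then:

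- HR slope = ρ × 24 / 10.5
- Drug coefficient = true drug effect + 10.9 × HR slope (the drug moves HR by −10.9, and the model subtracts slope × −10.9)

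At ρ = −0.3, where larger HR falls go with larger exercise gains, the slope is −0.3 × 24 / 10.5 = −0.686 points per bpm. The drug coefficient shifts by −0.686 × 10.9 = −7.5 points. At ρ = +0.3 the shift is +7.5 points.

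**Simulation.** The HR effect on exercise and the drug effect on exercise are both zero. An unmeasured common cause induces ρ. The plan's two strata are in the model, and beta-blocker use is set at one half (assumption).

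| Absolute ρ | HR term p < 0.05 | Size of shift in drug coefficient (points) |
|---|---|---|
| 0 | about 5% | 0 |
| 0.1 | about 11% | 2.5 |
| 0.2 | about 29% | 5.0 |
| 0.3 | about 58% | 7.5 |
| 0.4 | about 84% | 10.0 |

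The rates in the middle column do not depend on the sign of ρ. The HR-adjusted drug term also rejects too often: in about 10%, 18% and 28 to 30% of trials at |ρ| 0.2, 0.3 and 0.4, although the drug has no effect on exercise.

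**If the drug truly adds 22 points, none of it through HR.** With negative ρ the drug coefficient falls to 19.5 / 17.0 / 14.5 / 12.0 at |ρ| 0.1 / 0.2 / 0.3 / 0.4. At 0.3, 7.5 / 22 = 34% of the effect would look explained by HR when none is.

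**Two checks.** When the common cause is added to the model, the HR term rejects in 4.5 to 5.3% of trials, so the excess comes from leaving it out. The randomised comparison without HR change rejects in 4.7 to 4.9% of trials when the drug has no effect, and keeps about 90 to 91% power at a 22-point effect.

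**Limit.** These figures are for the ANCOVA branch. A Quade test with HR change as a covariate compares arms on rank residuals and gives no test of the HR term, so in that branch the stated question would go unanswered.

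**The case against.** The other side has several good points, and most of them stand.

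- **The randomised analysis is already planned.** The HR model is an additional step. A reader might infer that the secondary endpoint is compromised; it is not.
- **The plan does not promise a mechanism claim.** Mechanism is not a listed objective (1.2 to 1.4) or endpoint (11.3), and Section 1.1 calls the study Phase II/pilot. The p < 0.05 sentence recurs in near-identical form for other endpoints and is not tied to the HR term. A reader might infer that the plan will treat p < 0.05 as proof that HR drives exercise; the text leaves that possible but does not say it.
- **The rates are not type I error for an association.** The simulation builds in a real correlation, so the rates are power to detect it. They are false positives only for the causal question, which is the one 13.6 asks.
- **The bias has no fixed direction.** A reader might infer that the adjusted drug coefficient is always biased against the drug. That needs larger HR falls to go with larger exercise gains; the opposite correlation shifts it upward.
- **Some shared causes are partly handled.** Caffeine is barred for 24 hours before treadmill tests, uncontrolled illness is excluded, and pre-randomisation beta-blocker use is stratified. Changes during treatment are not covered by these.

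A reader might also add the treadmill stopping criterion in 5.3.3, 85% or more "of age-predicted maximal HR", as another source of a false link. It does not belong here. If a lower HR lengthens the test through that criterion, HR does affect measured duration, and the randomised comparison would be affected equally. That is a separate question.

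None of this answers the core point: 13.6 puts a causal question to a model that cannot answer it, without a caveat.

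**Conclusion.** The point holds in a limited form. As worded, the follow-on model in 13.6 could support a false conclusion that HR change affects exercise duration, and its drug coefficient does not estimate the randomised effect. The size rests on the assumed ρ: there is no excess at 0, about 29% significant HR terms at 0.2, and about 84% at 0.4. It also rests on linear ANCOVA, 27 evaluable patients per arm and the plan's SDs. The documents do not show what ρ is in this population, so they do not show that a false finding is likely, only that the plan has no protection against one. The consequence is confined to the interpretation of this one step.

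**What to change.** In Section 13.6:

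1. State that the model without HR change is the only test of the secondary endpoint, and that the p < 0.05 criterion refers to it.
2. Label the follow-on model exploratory and replace *affects* with *is associated with*, in line with 13.1.
3. Add baseline resting HR and baseline exercise duration as covariates. Both are already collected at the baseline visit.
4. Report the HR slope with its 95% CI.
5. State that no causal-mechanism or efficacy conclusion will be drawn from the HR slope or the HR-adjusted drug coefficient.

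Item 3 reduces confounding by baseline status but not by shared causes that arise after randomisation, so items 2 and 5 are still needed. The interval in item 4 carries the same information as a p-value; the protection comes from the label and the limit on conclusions.

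The cost is a few sentences of text, with no new data and no more patients. The trial gives up a causal mechanism claim that its design cannot support.

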Tilt tests predominantly evaluate adrenergic function by applying orthostatic stress. Patients will be placed in the supine position and baseline heart rate and blood pressure will be acquired over 5-10 minutes. The patient will then be tilted up to an angle of 70 degrees over 5-10 seconds. Patients will be closely observed for chest pain, shortness of breath, dizziness, lightheadedness or syncope. If they have no adverse reaction, the heart rate and blood pressure will be assessed every minute for 10 minutes. The patient will then be placed back in the supine position. The increase in heart rate and drop in blood pressure in response to the tilt will be recorded.¹⁹

4. Heart rate variability:

Heart rate variability with low frequency and high frequency oscillations in RR intervals assesses the balance of sympathetic and parasympathetic influences in the heart. Measures of overall heart rate variability and spectral analysis of heart rate variability will be performed with a Matlab based computer system.²⁰

5. Sudomotor testing

Electrochemical skin conductance (ESC) is a new noninvasive test for measurement of sudomotor functions.²¹ ESC correlates with loss of small fiber skin nerves, and it is useful for evaluation of small fiber neuropathy. Measurements using ESC will be performed as described previously.²²

The RSA and Valsalva ratio will be compared to age and gender based normative values (Tables 1 and 2). The cardiovagal composite autonomic severity score (CASS) will be calculated (Table 3). The adrenergic CASS will be calculated (Table 4).¹⁹

Table 1: Normal Values for Deep Breathing Test

Age range (years)	Minimum Normal RSA (beats/min)
10-29	≥ 14
30-39	≥ 12
40-49	≥ 10
50-59	≥ 9
60-69	≥ 7

Table 2: Normal Values for Valsalva Ratio

Age range (years)	Minimum Normal Valsalva Ratio	
	Women	Men
10-29	1.46	1.59
30-39	1.5	1.52
40-49	1.51	1.44
50-59	1.47	1.36
60-69	1.39	1.29

Table 3: Calculation of Cardiovagal Score

Result	Degree of Abnormality	Cardiovagal Score	Definition
Normal		0	
Abnormal	Mild	1	RSA or Valsalva ratio reduced but $\geq 50\%$ of minimal normal values
	Moderate	2	RSA or Valsalva ratio $< 50\%$ of minimal normal values
	Severe	3	Both RSA and Valsalva ratio $< 50\%$ minimal normal values

Table 4: Calculation of Adrenergic Score:

Result	Degree of Abnormality	Adrenergic Score	Definition
Normal	0		

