8.2 IND Agent #2: N/A

8.3 Other Agent #1: N/A

8.4 Other Agent #2: N/A

9. BIOMARKER, CORRELATIVE, AND SPECIAL STUDIES

9.1 Biomarker Studies: N/A

9.2 For IDE Protocols Only: Investigational Device Information: N/A

9.3 Laboratory Correlative Studies: N/A

9.4 Other Agent #2: N/A

10. STUDY CALENDAR

Baseline evaluations/tests are to be conducted within 1 week prior to start of protocol therapy. In the event that the participant's condition is deteriorating, laboratory evaluations should be repeated within 48 hours prior to initiation of therapy.

2 week study evaluations and drug up-titration should be administered within ± 3 days of the protocol-specified date, unless otherwise noted.

Week 6 study evaluations/tests should be conducted within ± 7 days of the protocol-specified date and should be completed prior to termination of study drug.

	Screening visit	Baseline	Week 2	Week 6
Agents:		Ivabradine vs. placebo	Ivabradine or placebo dose titration	Study End
Informed consent	X			
Demographics	X			
Medical history	X		X	X
Physical exam		X	X	X
Concurrent Meds	X	X	X	X
Vital signs	X	X	X	X
Height		X		X
Weight		X		X
Serum chemistry ^a	X			
EKG (as indicated)	X	X	X	X
B-HCG		X ^b		X ^b
Exercise stress test		X		X
24-hr ambulatory Holter monitor		X		X
SF-36 QOL questionnaire		X		X
Sophisticated autonomic function testing ^c		X		X
Adverse event evaluation		X-----X		
a: Review of SGOT [AST], SGPT [ALT], creatinine obtained within the last 12 months. b: Urine pregnancy test (women of childbearing potential). c: For subset of patients randomized to receive autonomic function testing				

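### The CASS comparison lists an adjustment factor that is constant in every patient analysed, and leaves out the baseline score that would add precision

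*Combined protocol and SAP*

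**What the plan says.** Section 13.6 (exploratory end-point 1) limits the autonomic end-point to a subset: "it will only be conducted in half the patients enrolled in the trial (n=30) and no power calculation has been made". Both scores are obtained at baseline and 6 weeks "for each patient in this substudy", and the outcome is a change score: "The change in CASS and adrenergic CASS will then be assessed for each patient". The arms are compared by "Quade test adjusting for the stratification factors (beta blocking agents [Yes, No], autonomic function testing [Yes, No]) (for ordinal data"), at two-sided p < 0.05.

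The scores come from the laboratory tests in Section 5.3.3(d). There, "The cardiovagal composite autonomic severity score (CASS) will be calculated (Table 3") from the deep-breathing and Valsalva results, and the adrenergic score comes from Valsalva and tilt (Table 4). The same section states that "a subset of patients (n=30) will undergo further sophisticated autonomic function testing at the baseline and 6 week visits". Footnote c of the Section 10 calendar marks these tests "For subset of patients randomized to receive autonomic function testing". Sections 13.1 and 13.3 make allocation to testing part of the four-way 1:1:1:1 randomisation within beta-blocker strata.

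**The concern.** An adjustment factor can only do something if it varies among the patients analysed. Autonomic testing (Yes/No) varies in the 60-patient analyses of heart rate, exercise duration and SF-36, where the same phrase appears. It cannot vary in the CASS analysis, because having a score requires having been tested. The phrase appears to have been carried over.

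Meanwhile baseline CASS, which is measured in the substudy and strongly tied to how far a score can move, is not a covariate. A patient who starts at 0 cannot improve, and one at the top of the scale cannot worsen. At stake are a plan that does not describe the adjustment actually made, and some lost precision in a comparison of about 15 patients per arm.

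**Working it through.** **1. Size of the analysis set.** Two of the four equal groups have autonomic testing: 60 × 2/4 = 30, which matches the stated n=30. On the 54-patient target it is 54 × 2/4 = 27, or about 14 per arm.

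**2. Can the factor take the value No?** CASS needs deep breathing, Valsalva and tilt, and only the subset randomised to testing has these. Under Section 13.1, a patient allocated to testing who cannot complete it continues with the other study procedures. That removes a score from the Yes group; it does not create one in the No group. The factor therefore has one level among patients with a CASS.

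**3. Effect of a one-level factor.** Quade's test ranks the outcome and covariates, regresses outcome ranks on covariate ranks, and compares the residuals between arms. With columns for intercept, beta-blocker and testing = Yes, the design matrix has 3 columns and rank 2, because the third is a multiple of the intercept. In 2,000 simulated datasets (15 per arm), the p-value with and without the constant term differed by at most 1.8 × 10⁻¹⁵, which is rounding error.

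**4. Why omitting baseline costs precision.** For a continuous score with equal variance σ² at both visits and correlation ρ, the change score has variance 2σ²(1−ρ). After adjustment for baseline the residual variance is σ²(1−ρ²). The ratio of adjusted to unadjusted is (1+ρ)/2: 0.70 at ρ = 0.4, 0.80 at 0.6 and 0.90 at 0.8. CASS is ordinal and bounded, so this shows the direction only. Simulation gives the size.

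**5. Simulation.** All of the following inputs are assumptions, since the documents give none: 15 per arm; latent bivariate normal scores cut at −0.5, 0.3 and 1.0 into four levels; a drug effect of 0.8 latent SD; 8 of 30 patients on beta-blockers; 5,000 runs per setting; two-sided 0.05.

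| Latent correlation | Power, beta-blocker only | Power, plus baseline CASS | Gain (points) | Type I error, without / with baseline |
|---|---|---|---|---|
| 0.3 | 0.294 | 0.457 | 16.3 | 0.057 / 0.059 |
| 0.5 | 0.365 | 0.505 | 14.1 | 0.054 / 0.055 |
| 0.7 | 0.496 | 0.628 | 13.2 | 0.051 / 0.051 |
| 0.9 | 0.755 | 0.837 | 8.2 | 0.049 / 0.050 |

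The simulation standard error is at most √(0.25/5000) = 0.007.

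**6. Sensitivity to the assumed effect.** With 14 per arm, correlations of 0.4–0.8 and several four-level distributions, the gain was about 8–16 points at a 0.8 SD shift and about 2–4 points at 0.4 SD. A separate run with 40/35/20/5% of patients per level (1,500 runs per setting) gave about 3–6 points at 0.4 SD and −1 to +2 points at 0.2 SD, where power was near 0.1 either way.

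**The case against.** The strongest reply is that nothing goes wrong numerically. A reader might infer from the impossible factor that the analysis cannot be carried out, or that its result would be biased. The documents support neither. The beta-blocker adjustment, the only stratification factor that varies in the subset, is still made. The constant term drops out under ordinary least squares. Randomisation protects the comparison whether or not baseline is included. All of this stands.

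Three further objections carry weight:

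- A change score does use the starting value, by subtracting it. What is missing is baseline as a covariate. Adding it does not remove the floor: patients at 0 still cannot improve.
- The omission is not peculiar to CASS. Sections 13.5 and 13.6 give no end-point a baseline covariate, so a repair to CASS alone would leave the end-points handled differently.
- The end-point is exploratory and no power is claimed for it, and the larger gains depend on a large assumed effect.

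These lower the priority. They do not justify keeping a factor that cannot vary, or leaving out a covariate that is already collected and costs nothing to use.

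**Conclusion.** The point holds in a limited form. That the autonomic-testing factor is redundant for CASS follows from the text alone and needs no assumption. As written, the test adjusts for beta-blocker use only; it can be run, and its type I error is close to nominal. Leaving out baseline CASS costs precision, not validity.

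The size of that loss rests on inputs absent from the documents. It is about 8–16 points of power if the latent effect is 0.8 SD, about 2–4 points at 0.4 SD, and negligible for smaller effects. To say that the plan wastes much of the substudy's information would go beyond this, because it is true only if the effect is large. The primary and secondary conclusions are unaffected. Low priority.

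**What to change.** In Section 13.6, exploratory end-point 1, remove the autonomic-testing factor, keep beta-blocking agents, and add the baseline value of the score being tested. The text could read: *Change in cardiovagal CASS and in adrenergic CASS will each be compared between arms by a Quade test with beta-blocker use and the ranked baseline value of the same score as covariates, among patients randomised to autonomic testing who have scores at both visits.*

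Keep the autonomic-testing factor in the analyses run on all patients, where it does vary. For consistency, consider baseline as a covariate for resting heart rate (13.5), exercise duration and SF-36 (13.6) as well.

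The cost is one line of analysis text, settled before unblinding. No new data, visits or patients are needed. A change score already requires the baseline value, so no patient is lost from the analysis.
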